5.2.3. Right censored Data

Not applicable.

5.2.4. Visit-specific censored Data

Not applicable.

5.3. Important protocol deviation not leading to elimination from per-protocol analysis set

The following important protocol deviations will be reported by groups:

- Forced randomization: in case of supplies shortage for the next assigned vaccine according to the randomization schedule at the clinical site, the randomization system will use the forced randomization procedure in order to continue to enrol and vaccinate subjects. The system moves seamlessly to the next treatment/randomization number for which vaccine supplies are available. The site will not be aware of the forced randomization event.

- Manual randomization: in case the randomization system is unavailable, the investigator has the option to perform randomization by selecting supplies available at the site according to a pre-defined rule.

6. STATISTICAL ANALYSES

Note that standard data derivation rule and stat methods are described in Annex 1 and will not be repeated below.

6.1. Demography

6.1.1. Analysis of demographics/baseline characteristics planned in the protocol

The distributions of subjects enrolled by centre will be tabulated by group.

The numbers of subjects who are withdrawn from the study will be tabulated by group according to the reason for withdrawal.

The median, mean, range and standard deviation (SD) of age at each study vaccine dose (in weeks) will be computed by group. The median, mean and SD of height in centimetre (cm) and weight in kilograms (kg) at Visit 1 will be computed by group. The Body Mass Index (BMI) at Visit 1 will also be computed as weight (in kg)/height² (in m). The gender composition per group will also be presented.

The deviations from specifications for age and intervals between study visits will be tabulated by group.

6.1.2. Additional considerations

The median, mean, range and standard deviation (SD) of gestational age (in weeks) will be computed by group.

6.2. Exposure

6.2.1. Analysis of exposure planned in the protocol

The number of doses of the liquid HRV vaccine and DPT-IPV vaccine administered will be tabulated per group.

6.2.2. Additional considerations

None.

6.3. Immunogenicity

6.3.1. Analysis of immunogenicity planned in the protocol

The ATP cohort for immunogenicity will be used for the primary analysis of immunogenicity. An analysis of immunogenicity based on the TVC will be performed

only if more than 5% of the vaccinated subjects with immunogenicity results available were excluded from the ATP cohort for immunogenicity. In such a case, the TVC analyses will evaluate whether exclusion from the ATP cohort has biased the results.

Within group assessment

For each treatment group and each antigen:

- Percentage of subjects with antibody concentrations/ titres greater than or equal to the pre-specified cut-off will be calculated with exact 95% CI (Refer Table 9 of the protocol). Anti-PT and anti-FHA antibody concentrations ≥ 10 IU/mL will also be calculated with exact 95% CI.
- GMC/GMTs, as applicable with 95% CIs will be computed.
- The distribution of antibody concentrations/ titres, as applicable, will be presented using reverse cumulative curves (RCCs).

Between group assessment

For each antigen in the DPT-IPV vaccine:

- The two-sided asymptotic standardised 95% CIs for the difference between groups (Co-administration group minus Staggered group) in terms of percentage of subjects with antibody concentrations/ titres greater than or equal to the pre-specified cut-off will be computed. Anti-PT and anti-FHA antibody concentrations ≥ 10 IU/mL will also be calculated with exact 95% CI.

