2. STUDY DESIGN

N = Number of subjects planned to be enrolled; n = Number of subjects in each group; BS = Blood Sampling. Visit 3 and Visit 5 are applicable only for subjects in the Staggered group. Visit 4 is applicable only for subjects in the Co-administration group.

- Experimental design: Phase IV, open-label, randomised, controlled, multi-centric, single-country study with two parallel groups.
- Primary Completion Date: Visit 7 (Month 5)
- End of Study: Last testing results released of samples collected at Visit 7
- Study groups: The study groups and epoch foreseen in the study are provided in Table 1.

Table 1 **Study groups and epochs foreseen in the study**

| Study Groups | Number of subjects | Age (Min/ - Max) | Epoch |
|-------------------------|--------------------|--------------------|-----------|
| | | | Epoch 001 |
| Co-administration group | 146 | 6 weeks - 12 weeks | x |
| Staggered group | 146 | 6 weeks - 12 weeks | x |

- The study groups and treatment foreseen in the study are provided in Table 2.

Table 2 Study groups and treatment foreseen in the study

| Treatment name | Vaccine name | Study Groups | |
|----------------|--------------|-------------------------|-----------------|
| | | Co-administration group | Staggered group |
| Rotarix | HRV | x | x |
| Squarekids | Squarekids | x | x |

- Control: active control (Staggered group).
- Vaccination schedules: The vaccination schedules are as follows:
 - Subjects in the Co-administration group will be administered the DPT-IPV vaccine according to a 3, 4, 6 month schedule and the liquid HRV vaccine according to a 2, 3 month schedule.
 - Subjects in the Staggered group will be administered the DPT-IPV vaccine according to a 3, 4.5, 6 month schedule and the liquid HRV vaccine according to a 2, 3.5 month schedule.
- Treatment allocation: Randomised 1:1 using GSK Biologicals' central randomisation system on Internet (SBIR). The randomisation algorithm will use a minimisation procedure accounting for centre and stratified for a HRV immunogenicity sub-cohort.
- Blinding: Open-label.
- Sampling schedule: Details of the samples to be collected are as follows:
 - A blood sample of approximately 2 mL will be collected from a sub-cohort of subjects, 1 month after the administration of the second dose of the liquid HRV vaccine.
 - A blood sample of approximately 5 mL will be collected at Visit 7, 1 month after administration of the last dose of DPT-IPV vaccine from all the subjects.

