| 2120 | Obvious incoherence, abnormal serology evolution or error in data (Eg; incoherence between CRF and results, wrong sample labelling) |

Table 4 Intervals between study visits for code 2080 and 2090

| Study Group | Interval | Optimal length of interval ¹ | Allowed interval ² |
|-------------------------|-------------------|---|-------------------------------|
| Co-administration group | Visit 1→Visit 2* | 30 days | 28 days - 42 days |
| | Visit 2→Visit 4 | 30 days | 28 days – 42 days |
| | Visit 4→Visit 6 | 56 days | 28 days - 56 days |
| | Visit 6→Visit 7 | 30 days | 21 days - 48 days |
| Staggered group | Visit 1→Visit 2* | 30 days | 28 days - 42 days |
| | Visit 2→Visit 3 | 15 days | 7 days - 21 days |
| | Visit 3→Visit 5** | 30 days | 28 days - 42 days |
| | Visit 5→Visit 6 | 45 days | 28 days – 56 days |
| | Visit 6→Visit 7 | 30 days | 21 days - 48 days |

¹. Whenever possible the investigator should arrange study visits within this interval.

². Subjects will not be eligible for inclusion in the According To Protocol (ATP) cohort for analysis of immunogenicity if they make the study visit outside this interval.

* Visit 2 should take place when the subject is 3 months of age or older.

**The period between Visit 2 and Visit 5 should be within 8 weeks.

There should be a time-period of at least 7 days between the administration of an inactivated vaccine and any other vaccine, and 28 days between the administration of a live virus vaccine and any other vaccine, in Japan. Please refer to the package inserts of *Rotarix* and *Squarekids* for more details.

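### The TVC re-analysis of the non-inferiority comparison depends on a pooled 5% exclusion rate, so up to 14 of 292 infants can be left out of the primary analysis with no pre-specified check of their effect on the result

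*SAP*

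**What the plan says.** Section 6.3.1 of the SAP sets the analysis population: "The ATP cohort for immunogenicity will be used for the primary analysis of immunogenicity". The seven between-group criteria in section 3.1, each with a limit of -10 percentage points, are therefore judged on that cohort.

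A TVC immunogenicity analysis follows "only if more than 5% of the vaccinated subjects with immunogenicity results available were excluded from the ATP cohort for immunogenicity". Its purpose is stated: "In such a case, the TVC analyses will evaluate whether exclusion from the ATP cohort has biased the results". The rule names one percentage of vaccinated subjects with results and does not say that it applies within each group.

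Other relevant parts of the SAP:

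- Section 2 plans 146 infants per arm, allocated 1:1, with "Blinding: Open-label".
- Section 5.2.2 lists the exclusion codes. Table 4 there gives visit windows that differ by arm: four for Co-administration, and five for Staggered with the added footnote "The period between Visit 2 and Visit 5 should be within 8 weeks".
- Section 6.1.1 tabulates deviations in age and visit intervals by group. Template 5 tabulates ATP exclusions by code and by group.
- Section 6.3.2 adds one other sensitivity analysis of the primary objectives. It concerns forced randomisation and does not address ATP exclusions.

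**The concern.** Bias in a difference between two arms depends on which infants are excluded and from which arm. The total number excluded is a weak guide to it. The trial is open-label, and some exclusion codes call for judgement, such as an infection that may have influenced the immune response (2060, 2070) or an abnormal serology evolution (2120). With about 146 infants per arm and high expected response rates, a handful of non-responders moves the lower confidence limit by several points.

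The plan recognises the risk and names the analysis that would examine it, then makes that analysis conditional on a pooled rate. At or below 5%, the non-inferiority result would be reported with no pre-specified evidence on whether it depends on the exclusions. A TVC analysis run later, because the exclusion tables looked uneven, would be post hoc.

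**Working it through.** **Inputs.** From the SAP: 146 infants per arm, 292 in total (section 2, Table 1); trigger above 5% (6.3.1); limit of -10 points on the lower bound of a two-sided 95% standardised asymptotic interval, Co-administration minus Staggered (3.1, 11.1). The SAP gives no sample-size or power figure to reproduce. All response counts below are assumptions.

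**Interval check.** A score interval for the difference, with the N/(N-1) variance factor, returns -2.25 and 2.30 for 219/219 v 214/214 at 97.5%. These are the mock figures in Template 15, at the level given in its footnote. Leaving the factor out changes the limits below by no more than 0.02 points and changes no pass or fail.

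**Step 1: how many exclusions escape the trigger.**

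- 0.05 × 292 = 14.6, so 14 is the largest number that does not trigger.
- 14/292 = 4.79%; 15/292 = 5.14%.
- All 14 in one arm: 14/146 = 9.59%. This assumes that all 292 infants have results. With 140 per arm the ceiling is 14/140 = 10.0%.

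**Step 2: can the conclusion reverse below the trigger?** Take 10 exclusions in Co-administration and 4 in Staggered, 14 in all. Assume that 3 of the 10 and none of the 4 are non-responders.

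| Set | Co-administration | Staggered | Difference | Lower limit | Result |
|---|---|---|---|---|---|
| ATP | 130/136 | 140/142 | -3.00 | -8.07 | pass |
| TVC | (130+7)/146 = 137/146 | (140+4)/146 = 144/146 | -4.79 | -10.12 | fail |

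**Step 3: how delicate is that example?**

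- With 2 non-responders among the 10: 138/146 v 144/146, lower limit -9.26, pass.
- With 3 among the 10 and 1 among the 4 in Staggered: 137/146 v 143/146, lower limit -9.52, pass.

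**Step 4: the extreme.** All 14 exclusions in Co-administration and no other failures: ATP 132/132 v 146/146, lower limit -2.84, pass. If 8 of the 14 are non-responders: TVC 138/146 v 146/146, lower limit -10.45, fail. If 7 are: 139/146 v 146/146, lower limit -9.58, pass.

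**Step 5: would a trigger within each arm be enough?** It would allow floor(0.05 × 146) = 7 exclusions per arm (7/146 = 4.8%). Take 7 and 7, the same TVC counts as in step 2, and 3 non-responders among the 7 from Co-administration:

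- ATP: (137-4)/139 = 133/139 v (144-7)/139 = 137/139, lower limit -7.85, pass.
- TVC: 137/146 v 144/146, lower limit -10.12, fail.

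A per-arm trigger would also stay silent here.

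**The case against.** The rule is coherent: it is fixed in advance, has a stated purpose, and appears under a heading that refers to the protocol, which is not at hand. It contradicts nothing else in the SAP. That stands, so this is an improvement to the plan and not the correction of an error.

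The illustration is selected. It needs 3 non-responders among 10 excluded infants, when the ATP rate in that arm is 6/136 = 4.4%. At that rate, three or more of ten has a probability of about 0.8%. The result misses the limit by only 0.1 point, and step 3 shows how easily it returns to a pass. This also stands. It limits the example to showing that reversal is possible. The excluded infants need not share the ATP response rate, however, and whether they do is what the TVC analysis is meant to examine.

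A reader might infer three stronger points that the SAP does not support:

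- **That imbalance would go unseen.** It would not. Section 6.1.1 and Template 5 display deviations and exclusions by group. What is missing is the re-analysis.
- **That the different visit windows in Table 4 make a false pass likely.** The Staggered arm has more windows, so if anything one would expect more exclusions there. Removing non-responders from Staggered raises its ATP rate and makes non-inferiority harder to show. The Visit 2 to Visit 5 cap is also not an independent sixth window: the two windows it spans add to at most 21 + 42 = 63 days, so the 56-day cap adds exclusions only for sums of 57 to 63 days.
- **That applying the trigger within each arm would cure the problem.** Step 5 shows that a 7/7 split still escapes.

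**Conclusion.** The point holds as a modest, inexpensive improvement. Section 6.3.1 allows up to 14 of 292 infants (4.8%) to be excluded from an open-label non-inferiority analysis without the bias check that the same section describes. The count assumes that all planned infants have results. The 9.6% figure further assumes that every exclusion falls in one arm, and should not be read as an expected rate. A reversal from -8.1 to -10.1 below the trigger is arithmetically possible under assumed response counts close to the limit, and nothing in the SAP shows that it is probable. The weakness is that the check is conditional at all. Pooling over arms makes it worse but is not the whole cause.

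**What to change.** In section 6.3.1, remove the 5% condition for the primary between-group comparison. State that the difference and its 95% interval for each of the seven criteria in section 3.1 will always be reported on the TVC, for infants with a Visit 7 result, beside the ATP analysis. Label it a supportive sensitivity analysis, so that the confirmatory decision remains with the ATP cohort. The 5% condition may stay for the remaining descriptive immunogenicity tables.

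The TVC immunogenicity analysis is already defined in section 5.1.1, and section 2 plans a Visit 7 sample from every infant, so no new data are needed. The cost is one extra set of tables. No further reporting of exclusions by arm is required, because it is already planned.

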6.3.2. Additional considerations

The following seropositivity thresholds are applicable:

- anti-RV IgA antibody concentration ≥ 20 U/mL.
- anti-diphtheria antibody concentrations \geq assay cut-off
- anti-tetanus antibody concentrations \geq assay cut-off
- anti-PT antibody concentrations ≥ 2.693 IU/mL
- anti-FHA antibody concentrations ≥ 2.046 IU/mL

The following seroprotection thresholds are applicable:

- anti-diphtheria antibody concentrations ≥ 0.1 IU/ml;
- anti-tetanus antibody concentrations ≥ 0.1 IU/ml;
- anti-poliovirus types 1, 2 and 3 antibody titres ≥ 8 .

Other cut-offs to be considered for summary tables and between-group comparisons

- Anti-PT antibody concentrations ≥ 10 IU/mL
- Anti-FHA antibody concentrations ≥ 10 IU/mL

Anti-rotavirus IgA antibody GMCs and their 95% CI will also be computed on subjects seropositive for anti-rotavirus IgA antibody.

A sensitivity analysis excluding forced randomization will be performed for the primary objectives in case the percentage of forced randomizations exceed 5% (forced randomizations are allocation which were constrained by supply available at the site. In open studies, allocations without using the randomization system are also forced randomizations).

6.4. Analysis of safety

6.4.1. Analysis of safety planned in the protocol

The safety analysis will be based on the TVC.

The incidence by dose, overall per dose and overall per subject, with its exact 95% CI of

- any adverse event (solicited or unsolicited, local or general),
- at least one local adverse event (solicited or unsolicited), and,
- at least one general adverse event (solicited or unsolicited),

during the 8-day (Days 0-7) follow-up period will be tabulated. The same calculations will be performed for any Grade 3 (solicited or unsolicited) symptoms, related and for any adverse event requiring medical attention.

For each type of solicited symptom, the incidence during the 8-day (Days 0-7) follow-up period of the symptom (any grade, Grade 3, related, Grade 3 related, requiring medical advice) will be tabulated as follows:

- at each dose, the percentage of doses followed by the reporting of a symptom and its exact 95% CI,
- over all the doses, the percentage of subjects reporting the symptom and its exact 95% CI,
- over all the doses, the percentage of doses followed by the reporting of a symptom and its exact 95% CI,
- for fever, additional analyses will be performed by 0.5°C increments.

The percentage of subjects who receive concomitant medication, who receive antipyretic medication and prophylactic antipyretic medication during the 8-day (Days 0-7) and 31-day (Days 0-30) follow-up period post-vaccination will be tabulated by dose, overall per subject and over all the doses.

The verbatim reports of unsolicited symptoms will be reviewed by a physician and the signs and symptoms will be coded according to MedDRA. Every verbatim term will be matched with the appropriate Preferred Term. The percentage of subjects with unsolicited symptoms occurring during the 31 days (Days 0-30) with its exact 95% CI will be

tabulated by preferred term. Similar tabulation will be done for Grade 3 unsolicited symptoms and for unsolicited symptoms causally related to vaccination.

Subjects who experienced at least one SAE during the entire study period (from the first dose till the end of the study [Visit 7]) will be reported and the SAEs will be described in detail.

6.4.2. Additional considerations

- In line with the endpoint description separate analysis will be made for solicited symptom, unsolicited AE within 31 days post vaccination and concomitant medication for
 - The 2 HRV doses
 - The first DTPa-IPV dose
- In line with the HRV project standard, the primary analysis of solicited symptom will be performed by administered dose regardless of whether a solicited symptom has been documented as present/absent. A complementary analysis by documented dose in which only dose for which presence/absence of the symptoms is recorded will be performed in case the percentage of documented dose among administered dose exceed 5% for one visit or a group.
- The incidence by dose, overall per dose and overall per subject of any grade 3 adverse event (solicited or unsolicited, local or general) with causal relationship to vaccination during the 8-day (Days 0-7) follow-up period will be tabulated with exact 95% CI.
- The percentage of subjects with unsolicited symptoms requiring medical attention occurring within 31 days (Days 0-30) post-vaccination with its exact 95% CI will be tabulated by group and preferred term. Similar tabulation will also be done for unsolicited AEs rated as grade 3 in intensity with causal relationship to vaccination.
- The percentage of subjects with causally related AEs from the first study vaccine until Visit 7 will be tabulated by group and preferred term.
- Medications will be coded using the GSKDRUG dictionary. Medications which started during the specified periods (Days 0-7 and Days 0-30) will be counted rather than all medications taken during the specified periods.
- For clinicaltrials.gov and EudraCT posting purposes, a summary of subjects with all combined solicited (regardless of their duration) and unsolicited adverse events will be provided. Solicited adverse events will be coded by MedDRA as per the following codes:

| Solicited symptom | Lower level code | Lower level term |
|----------------------------|------------------|---------------------------|
| Pain at injection site | 10022086 | Injection site pain |
| Redness at injection site | 10022098 | Injection site redness |
| Swelling at injection site | 10053425 | Injection site swelling |
| Fever | 10016558 | Fever |
| Irritability/Fussiness | 10057224 | Irritability postvaccinal |

| Solicited symptom | Lower level code | Lower level term |
|-------------------|------------------|------------------|
| Diarrhoea | 10012727 | Diarrhea |
| Vomiting | 10047700 | Vomiting |
| Loss of appetite | 10003028 | Appetite lost |
| Cough/ runny nose | 10011224 | Cough |
| Drowsiness | 10013649 | Drowsiness |

[figure not shown]

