3.2. Secondary objectives

- To assess the immunogenicity of the liquid HRV vaccine in terms of serum anti-RV IgA antibody seropositivity and Geometric Mean Concentrations (GMCs) in a sub-cohort of subjects, 1 month after the second dose of the liquid HRV vaccine.
- To assess the immunogenicity to all the antigens contained in the DPT-IPV vaccine in terms of GMCs/ geometric mean antibody titres (GMTs), 1 month after the third dose of the DPT-IPV vaccine.
- To assess reactogenicity and safety after each dose of liquid HRV vaccine and first dose of DPT-IPV vaccine in terms of solicited symptoms during the 8-day follow-up period and unsolicited symptoms during the 31-day follow-up period.
- To assess safety in terms of serious adverse events (SAEs) from the first dose of study vaccine up to study end.

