11.2.5. Safety

- For analysis of solicited, unsolicited adverse events (such as serious adverse events or adverse events by primary MedDRA term) and for the analysis of concomitant medications, all vaccinated subjects will be considered. Subjects who did not report the event or the concomitant medication will be considered as subjects without the event or the concomitant medication respectively.

- In case there will be more than 5% of subjects without documented dose for solicited symptoms (i.e., symptom screen not completed), sensitivity analysis will include only vaccinated subjects for doses with documented safety data (i.e., symptom screen completed).
- The following rules will be used for the analysis of solicited symptoms:
 - Subject who didn't document the presence or absence of a solicited symptom after one dose will be considered not having that symptom after that dose in the analysis done on "administered dose"
 - Subjects who documented the absence of a solicited symptom after one dose will be considered not having that symptom after that dose.
 - Subjects who documented the presence of a solicited symptom and fully or partially recorded daily measurement over the solicited period will be included in the summaries at that dose and classified according to their maximum observed daily recording over the solicited period.
 - Subjects who documented the presence of a solicited symptom after one dose without having recorded any daily measurement will be considered as having that symptom after that dose).
- The maximum intensity of local injection site redness/swelling will be coded as follows:

| Grade | Redness/swelling |
|-------|-------------------------|
| 0 | Absent |
| 1 | > 0 mm and \leq 5 mm |
| 2 | > 5 mm and \leq 20 mm |
| 3 | > 20 mm |

- For the analysis, temperatures will be coded as follows for oral, axillary or tympanic route:

| Grade | Temperature |
|-------|-------------------------------|
| 0 | < 37.5°C |
| 1 | \geq 37.5°C - \leq 38.0°C |
| 2 | > 38.0°C - \leq 39.0°C |
| 3 | > 39.0°C |

For rectal route, temperatures will be converted to axillary setting by subtracting 0.5°

- Note that for all tables described in this section, the way the percentage of subjects will be derived will depend on the event analysed (see table below for details). As a result, the N value will differ from one table to another.

| Event | N used for deriving % per subject for Vaccination phase | N used for deriving % per dose for Vaccination phase |

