|---------------------------|--|--|
| Concomitant vaccination | All subjects with study vaccine administered | All study visits with study vaccine administered |
| Solicited general symptom | Primary analysis: all subjects with study vaccine administered Sensitivity analysis: all subjects with at least one solicited general symptom documented as either present or absent (i.e., symptom screen completed) | Primary analysis: all study visits with study vaccine administered Sensitivity analysis: all study visits with study vaccine administered and with at least one solicited general symptom documented as either present or absent (i.e., symptom screen completed) |
| Solicited local symptom | Primary analysis: all subjects with study vaccine administered Sensitivity analysis: all subjects with at least one solicited local symptom documented as either present or absent (i.e., symptom screen completed) | Primary analysis: all study visits with study vaccine administered Sensitivity analysis: all study visits with study vaccine administered and with at least one solicited local symptom documented as either present or absent (i.e., symptom screen completed) |
| Unsolicited symptom | All subjects with study vaccine administered | All study visits with study vaccine administered |
| Concomitant medication | All subjects with study vaccine administered | All study visits with study vaccine administered |

- All CI computed will be two-sided 95% CI.

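### The primary solicited-symptom rates count undocumented doses as symptom-free, and the documented-dose analysis that would show the effect is only conditional

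*SAP*

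**What the plan says.** Reactogenicity is a secondary objective (SAP 3.2): "To assess reactogenicity and safety after each dose of liquid HRV vaccine and first dose of DPT-IPV vaccine in terms of solicited symptoms". Three provisions fix how it is analysed.

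- Section 6.4.2, which gives consistency across HRV studies as its reason: "the primary analysis of solicited symptom will be performed by administered dose regardless of whether a solicited symptom has been documented as present/absent".
- Section 11.2.5 applies this to a subject who did not "document the presence or absence of a solicited symptom after one dose will be considered not having that symptom after that dose", for the administered-dose analysis.
- The denominator table in 11.2.5 gives, for percentages per subject: "Primary analysis: all subjects with study vaccine administered". The per-dose row likewise takes all visits with vaccine administered.

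A second analysis on documented doses is also planned, and its trigger is stated in two ways. Section 6.4.2 says that it "will be performed in case the percentage of documented dose among administered dose exceed 5% for one visit or a group". Section 11.2.5 says "In case there will be more than 5% of subjects without documented dose for solicited symptoms", and in that case the "sensitivity analysis will include only vaccinated subjects for doses with documented safety data". Templates 22 and 23 are the mock tables for it.

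**The concern.** A dose with no symptom screen says nothing about whether symptoms occurred. Counting it as symptom-free fills missing safety data with the most favourable value, and the interval then treats those values as observed. For a safety objective the error can go only one way, towards lower incidence. The one reason given is consistency with a project standard. For immunogenicity the same SAP takes the other course: section 11.2.4 leaves missing measurements unreplaced.

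The planned check is conditional. Under the 11.2.5 trigger, a rate with up to 5% of subjects' data imputed as absent may be reported with no documented-dose figure next to it. If documentation differs between the groups, which are open-label and on different visit schedules, part of any visible difference in rates could come from documentation alone.

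**Working it through.** **Inputs from the SAP.** The planned size is 146 per group (section 2: "Co-administration group | 146", and the same for the Staggered group). Intervals are two-sided 95% Clopper-Pearson (11.1). The SAP gives no expected symptom rate and no expected undocumented share, so there is no planned figure to reproduce. As a check of the interval method only, the example data in the mock tables reproduce: 29/34 = 85.3% (68.9 to 95.0) and 165/508 = 32.5% (28.4 to 36.7).

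**Assumed quantities.** Let p be the symptom rate in documented doses, q the rate in undocumented doses and u the undocumented share. All three are assumptions.

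**Bias.**
- True rate = p(1 − u) + qu.
- Expected administered-dose rate = p(1 − u), because undocumented doses contribute no events.
- Bias = −qu. It is never upward, and it is zero if u = 0 or q = 0.
- Expected documented-dose rate = p. Its error is p − [p(1 − u) + qu] = u(p − q), which is zero only if q = p.

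**Size when q = p.** The true rate is then p. Coverage is the probability, with X ~ Binomial(146, p(1 − u)), that the exact interval contains p, summed over all X.

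| True rate | u | Expected reported rate | Coverage of 95% CI |
|---|---|---|---|
| 40% | 0% | 40.0% | 95.8% |
| 40% | 2% | 0.40 × 0.98 = 39.2% | 95.4% |
| 40% | 5% | 0.40 × 0.95 = 38.0% | 93.3% |
| 40% | 10% | 0.40 × 0.90 = 36.0% | 85.1% |
| 60% | 2% | 0.60 × 0.98 = 58.8% | 94.8% |
| 60% | 5% | 0.60 × 0.95 = 57.0% | 89.8% |
| 60% | 10% | 0.60 × 0.90 = 54.0% | 71.1% |

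For a less frequent symptom the effect is smaller: at a true 20%, coverage is 95.5% at u = 5% and 92.9% at u = 10%.

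**Other values of q.** In the extreme q = 1, the bias is −u, or −5 points at u = 5%. At q = 0 the administered-dose rate is exact and the documented-dose rate is too high by up: 0.40 × 0.05 = 2 points at p = 40% and u = 5%.

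**Unequal documentation.** With a true 40% in both groups and u = 1% in one and 5% in the other, the expected rates are 39.6% and 38.0%, an artificial gap of 1.6 points.

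**When the check runs.** Under 11.2.5 it is required only above 5% of subjects without a documented dose. Under 6.4.2, read literally, it runs when documented doses exceed 5% of administered doses, which would nearly always be so. The two conditions differ in direction and in unit (subjects against doses), so the SAP does not settle whether the check is produced at a low undocumented share.

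**The case against.** The strongest reply is that this is a disclosed convention with a planned check, applied to a descriptive endpoint. Section 7 rules out comparative analyses without a success criterion, so no conclusion of the trial turns on these rates. The safety analysis uses the total vaccinated cohort, and 11.2.5 treats non-reporting of unsolicited events and medications in the same way. Template 18 already plans a display of symptom-sheet compliance by dose and group, though its mock covers general symptoms only. At 5% undocumented, the 2-point shift on a true 40% is small beside an exact interval of roughly 32% to 48% at 146 subjects. All of this stands, and it limits the weight of the point.

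Two stronger readings are tempting, and the document supports neither. A reader might infer that the reported rates are always biased and every interval is centred on the wrong value. That requires some doses to be undocumented and some of those to have had symptoms; the SAP gives neither figure, and at 2% undocumented coverage is close to nominal. A reader might also infer that the documented-dose rate is the correct one and must become primary. It is unbiased only if documentation is unrelated to symptoms. If families of symptom-free infants complete the screen less often, it is too high and the administered-dose rate may be the closer of the two.

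What the reply does not answer is why the check should be conditional at all, on triggers that disagree.

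**Conclusion.** The point holds in limited form. The administered-dose rate is biased downward by qu, and the exact interval ignores this. The effect is negligible at about 2% undocumented, modest at 5%, and material at 10% for common symptoms. These sizes rest on assumed symptom rates, assumed undocumented shares and equal symptom rates in documented and undocumented doses. The defect is not the choice of primary analysis, which is defensible for continuity with earlier HRV trials. It is that the comparison a reader needs is not guaranteed: under 11.2.5 it can be omitted at 5% or less, and 6.4.2 sets a different condition. This is a cheap improvement. It does not affect the primary objective.

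**What to change.** In sections 6.4.2 and 11.2.5:

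1. Drop the 5% condition and always report the documented-dose analysis (Templates 22 and 23) beside the administered-dose analysis. This also removes the conflict between the two triggers.
2. Show the number and percentage of documented doses by group and visit, for local as well as general symptoms.
3. State that the administered-dose rate is a lower bound, and that the documented-dose rate assumes documentation is unrelated to symptoms.

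The sponsor can keep either analysis as primary. The cost is a change of SAP wording and a few extra tables whose layouts are already mocked.
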